6.3 SUBJECT SETS ANALYSED

Subject sets will be used as defined in the CTP, Section 7.3.

Table 6.3: 1 Subject sets analyzed

Class of endpoint	Subject set	
	TS	PKS
Primary PK endpoints		X
Secondary PK endpoints		X
Safety parameters & treatment exposure	X	
Demographic/baseline endpoints	X	

6.5 POOLING OF CENTRES

This section is not applicable, because the study was performed in only one centre.

6.6 HANDLING OF MISSING DATA AND OUTLIERS

Data of screened subjects who were withdrawn from the trial prior to first administration of any study drug will not be reported in the CTR.

Data of subjects who failed to complete all periods of the study (dropouts or withdrawals) will be reported in the CTR as far as their data are available. All withdrawals will be documented and the reason for withdrawal reported in the CTR.

CTP: *It is not planned to impute missing values for safety parameters.*

One exception where imputation might be necessary for safety evaluation are AE dates. Missing or incomplete AE dates are imputed according to BI standards (3).

Missing data and outliers of PK data are handled according to BI standards (4).

CTP: *PK parameters that cannot be reasonably calculated based on the available drug concentration-time data will not be imputed.*

6.7 BASELINE, TIME WINDOWS AND CALCULATED VISITS

A separate baseline is defined for each study treatment:

- Baseline for the treatment in the first treatment period is defined as the last available off-treatment value before administration of the respective formulation of BI 1358894.
- Baseline for the treatment in the second and third treatment periods is defined as the last available pre-dose value measured on or after Day 14 of the preceding visit.

Time windows are defined in Section 6.1 of the CTP. Adherence to time windows will be checked at the Report Planning Meeting.

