The following safety measures will be applied in this study in order to minimize the risk for healthy volunteers:

Proprietary confidential information © 2019 Boehringer Ingelheim International GmbH or one or more of its affiliated companies

- The dose selected for the current study was already investigated in the FIH SRD study. A higher dose was also investigated and was well tolerated.
- Adequate safety monitoring will be performed (e.g. vital signs (including blood pressure and pulse rate), ECGs, safety laboratory tests including CRP, ESR, hormone parameters, suicidality assessment and assessment of adverse events)
- Subjects will be hospitalized from Day 1 up to Day 4 of each treatment period and will be discharge only after a formal assessment and confirmation of fitness by an investigator or qualified designee. During the in-clinic stay, the subjects will be under medical observation and thoroughly monitored for both expected and unexpected events.

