#### 5.2.3 Safety laboratory parameters

For the assessment of laboratory parameters, blood and urine samples will be collected by the trial site at the times indicated in the [Flow Chart](#) after the subjects have fasted for at least 10 h. For retests, at the discretion of the investigator or designee, overnight fasting is not required.

The parameters that will be determined are listed in [Tables 5.2.3: 1](#) and [5.2.3: 2](#). Reference ranges will be provided in the ISF, Section 10.

Manual differential white blood cell count or urine sediment examinations will only be performed if there is an abnormality in the automatic blood cell count or in the urinalysis, respectively.

Table 5.2.3: 1 Routine laboratory tests

Functional lab group	BI test name [comment/abbreviation]	A	B	C
Haematology	Haematocrit	X	X	X
	Haemoglobin	X	X	X
	Red Blood Cell Count/Erythrocytes	X	X	X
	Reticulocytes count	X	X	X
	White Blood Cells/Leucocytes	X	X	X
	Platelet Count/Thrombocytes (quant)	X	X	X
	Erythrocyte Sedimentation Rate (ESR)	X	X	X
Automatic WBC differential, relative and absolute	Neutrophils; Eosinophils; Basophils; Monocytes; Lymphocytes	X	X	X
Manual differential WBC (if automatic differential WBC is abnormal and clinically relevant in the opinion of the investigator)	Polymorphnuclear neutrophils (segs); band neutrophils (stabs); eosinophils; basophils; monocytes; lymphocytes			
Coagulation	Activated Partial Thromboplastin Time	X	X	X
	Prothrombin time – INR (International Normalization Ratio)	X	X	X
	Fibrinogen	X	X	X
Enzymes	AST [Aspartate transaminase] /GOT, SGOT	X	X	X
	ALT [Alanine transaminase] /GPT, SGPT	X	X	X
	Alkaline Phosphatase	X	X	X
	Gamma-Glutamyl Transferase	X	X	X
	Glutamate Dehydrogenase (GLDH)	X	X	X
	Creatine Kinase [CK]	X	X	X
	Creatine Kinase Isoenzyme MB [only if CK is elevated]	X	X	X
	Lactic Dehydrogenase	X	X	X
	Lipase	X	X	X
	Amylase	X	X	X
Hormones	Thyroid Stimulating Hormone	X	--	X
	Free T3 - Triiodothyronine	X	--	X
	Free T4 – Thyroxine	X	--	X
Substrates	Glucose (Plasma)	X	X	X
	Creatinine	X	X	X
	Bilirubin, Total	X	X	X
	Bilirubin, Direct	X	X	X
	Protein, Total	X	X	X
	Albumin (Protein Electrophoresis)	X	--	--
	Alpha-1-Globulin (Protein Electrophoresis)	X	--	--
	Alpha-2-Globulin (Protein Electrophoresis)	X	--	--
	Beta-Globulin (Protein Electrophoresis)	X	--	--
	Gamma-Globulin (Protein Electrophoresis)	X	--	--
	C-Reactive Protein (Quant)	X	X	X
	Uric Acid	X	X	X
	Cholesterol, total	X	X	X
	Triglyceride	X	X	X

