**Table 5.2.3: 1      Routine laboratory tests (cont.)**

Functional lab group	BI test name [comment/abbreviation]	A	B	C
Electrolytes	Sodium Potassium Calcium	X X X	X X X	X X X
Urinalysis (Stix)	Urine Nitrite (qual) Urine Protein (qual) Urine Glucose (qual) Urine Ketone (qual) Urobilinogen (qual) Urine Bilirubin (qual) Urine RBC/Erythrocytes (qual) Urine WBC/Leucocytes (qual) Urine pH	X X X X X X X X	X X X X X X X X	X X X X X X X X
Urine sediment (microscopic examination if erythrocytes, leukocytes nitrite or protein are abnormal in urine)	Only positive findings will be reported (for instance, the presence of sediment bacteria, casts in sediment, squamous epithelial cells, erythrocytes, leukocytes)			

A: parameters to be determined at Visit 1 (screening examination)

B: parameters to be determined at Visit 2 on Day -3 to Day -1, unless screening examination is performed  
between Day -3 and Day -1, and at Visits 2/3/4 on Day 1, Day 2, Day 7, Day 11 and Day 14 (for time points  
refer to [Flow Chart](#))

C: parameters to be determined at Visit 5 (end of trial examination)

The tests listed in [Table 5.2.3: 2](#) are exclusionary laboratory tests that may be repeated as required. The results will not be entered in the CRF/database and will not be reported in the CTR. Except for drug screening, it is planned to perform these tests during screening only. Drug screening will be performed at screening and prior to each treatment period.

Proprietary confidential information © 2019 Boehringer Ingelheim International GmbH or one or more of its affiliated companies

Table 5.2.3: 2      Exclusionary laboratory tests

Functional lab group	Test name
Drug screening (urine)	Amphetamine/MDA Barbiturates Benzodiazepine Cannabis Cocaine Methadone Methamphetamines/MDMA/XTC Opiates Phencyclidine Tricyclic antidepressants
Infectious serology (blood)	Hepatitis B surface antigen (qualitative) Hepatitis B core antibody (qualitative) Hepatitis C antibodies (qualitative) HIV-1 and HIV-2 antibody (qualitative)

To encourage compliance with alcoholic restrictions, a breath alcohol test (e.g. Alcotest®7410, Dräger AG, Lübeck, Germany) will be performed at screening and prior to each treatment period, and may be repeated at any time during the study at the discretion of an investigator or designee. The results will not be included in the CTR

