7.8.2 Laboratory data

The analyses of laboratory data will be descriptive in nature and will be based on BI standards "Display and Analysis of Laboratory Data" ([9](#)).

Analyses will be based on normalised values, which means transforming to a standard unit and a standard reference range. The original values will be analysed if the transformation into standard unit is not possible for a parameter.

Descriptive statistics of laboratory values over time and for the difference from baseline (see [Section 6.7](#)) will be provided. Frequency tables of changes between baseline and last value on treatment with respect to the reference range will be presented.

Possibly clinically significant abnormal laboratory values are only those identified either in the Investigator's comments or at the Report Planning Meeting at the latest. It is the Investigator's responsibility to decide whether a lab value is clinically significant abnormal or not. Standard or project-specific rules for flagging clinically significant values in an automated manner will not be applied in this study.

Clinically relevant findings in laboratory data will be reported as baseline conditions (prior to first administration of study treatment) or as AEs (after first administration of study treatment) if judged clinically relevant by the investigator, and will be analyzed as such.

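### As SAP 6.7 is written, scheduled TSH, free T3 and free T4 samples give no change from baseline in any subject dosed in two or three periods

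*SAP*

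**What the plan says.** - **Schedule.** Protocol Table 5.2.3: 1 marks the hormones for columns A and C and dashes column B: "Thyroid Stimulating Hormone X -- X" and "Free T3 - Triiodothyronine X -- X", with free T4 the same. The legend makes A the screening visit and C Visit 5. B is the pre-dose visit on Day -3 to -1 plus Days 1, 2, 7, 11 and 14 of Visits 2 to 4.
- **Purpose.** Protocol 1.4.2 counts these tests among the risk-minimisation measures: "safety laboratory tests including CRP, ESR, hormone parameters". Protocol 7.3.4 says that laboratory data will be evaluated for differences from baseline.
- **Baseline.** SAP 6.7 sets one baseline per treatment. For Period 1 it is the latest off-treatment value ahead of that dose. For the later periods: "Baseline for the treatment in the second and third treatment periods is defined as the last available pre-dose value measured on or after Day 14", with the day counted in the visit before. It gives no fallback to screening and no exception by parameter.
- **Phase.** SAP Table 6.1: 2, which covers safety laboratory data, has only screening and on-treatment phases. The last on-treatment phase runs to the end of participation. SAP 6.1 has laboratory data analysed by treatment period.
- **Output.** SAP 7.8.2 plans "Descriptive statistics of laboratory values over time and for the difference from baseline", referring to Section 6.7, and frequency tables of the change from baseline to last on-treatment value against the reference range.

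**The concern.** The baseline rule suits the column B tests. Flow Chart footnote 13 takes the Visit 3 and 4 pre-dose laboratory values from Day 14 of the visit before, and SAP 6.7 follows it. The three hormones are not drawn on Day 14, so the rule points to a sample that is never scheduled.

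Two hormone samples per subject are planned, and the natural use of them is the change from screening to end of trial. Followed exactly, the SAP cannot form that change for the subjects who matter most, namely those who received all three doses. Any hormone change table would hold only people who stopped after the first dose. A programmer who noticed would have to choose between an uninformative table and an undocumented departure from the stated rule.

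**Working it through.** The plan states no figure to reproduce. The check counts baseline/on-treatment pairs under the SAP's own rules.

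**Inputs**
- Scheduled hormone samples: one at Visit 1 and one at Visit 5 (Protocol Table 5.2.3: 1 and its legend).
- Visit 5 timing: Day 17 to 22 (Protocol Flow Chart).
- Periods: 3, with doses at least 17 days apart (Protocol 3.1 and 6.2.2).
- Baseline rule: SAP 6.7. Phase rule: SAP Table 6.1: 2.

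**Formula.** Pairs in a period = (number of on-treatment values in that period) × (1 if a permitted baseline exists, otherwise 0).

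**Subject dosed in three periods**

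| Period | Permitted baseline | On-treatment hormone values | Pairs |
|---|---|---|---|
| 1 | Screening value | 0 | 0 × 1 = 0 |
| 2 | None (nothing drawn from Day 14 of Visit 2 to the next dose) | 0 | 0 × 0 = 0 |
| 3 | None (nothing drawn from Day 14 of Visit 3 to the next dose) | 1 (Visit 5) | 1 × 0 = 0 |

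Total: 0 pairs per hormone.

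**Subject stopping after two doses.** Period 1: 0 × 1 = 0. Period 2: 1 × 0 = 0. Total 0.

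**Subject stopping after one dose and attending Visit 5.** Period 1: 1 × 1 = 1. Total 1.

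**Sensitivity.** The counts are the same with 17, 21 or 28 days between doses (17 is the protocol minimum; 21 and 28 are assumptions) and with Visit 5 on Day 17 or Day 22.

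**Check on the column B tests.** Each period has on-treatment values on Days 2, 7, 11 and 14, and Period 3 also has Visit 5. A baseline exists in every period, so the pairs are 4, 4 and 4 + 1 = 5. The gap is specific to tests scheduled only at Visits 1 and 5.

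**Where the Visit 5 values fall in by-treatment summaries.** The Period 3 row of Protocol Table 3.1 is C, B, A, D, C, A, D, B, E, E, A, D, which gives A 3, B 2, C 2, D 3, E 2. With 24 subjects on 12 sequences there are 2 per sequence, so the split is A 6, B 4, C 4, D 6, E 4 (total 24) if all complete.

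**With the screening value allowed as baseline.** Each subject with both samples gives 1 pair per hormone, so up to 24 × 1 = 24.

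**The case against.** The strongest reply is that little is lost, and much of it stands.

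- **Hormone review survives.** SAP 7 sorts the non-AE listings by sequence, subject and visit, so a subject's two hormone values appear together. Values over time can be summarised, and Protocol 7.3.4 compares laboratory data with reference ranges, which needs no baseline. Clinically relevant findings become AEs. SAP 7 also shows a missing category when values are missing, so a shift table might display end-of-trial categories against a missing baseline. That would still not be a shift.
- **No thyroid signal and no hypothesis.** Protocol 1.2.1 describes no thyroid finding, hormones are one item in a list of examples, and all safety analysis is descriptive. This limits the severity.
- **Other documents.** SAP 6.1 leaves technical detail to an ADS Plan, and SAP 7.8.2 relies on a sponsor laboratory standard. Neither is available here, and either might hold a convention for such tests. The gap in the SAP text is certain; that no change will be reported is not.
- **Unscheduled samples.** Protocol 6.2.3 has clinically relevant abnormal values monitored, so an extra hormone draw could happen to fall in the permitted window. None is planned.

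A reader might also infer that tabulating Visit 5 under the last treatment credits one formulation with a cumulative three-dose effect. The documents do not show such an effect. Protocol 1.2.2 gives a residual effect period of about 14 days. Visit 5 on Day 17 is 16 days after the third dose, at least 16 + 17 = 33 days after the second and at least 33 + 17 = 50 days after the first. Assigning late values to the last treatment is the SAP's convention for all laboratory and vital-sign data, not a fault peculiar to hormones. Nor will the listings be arranged by last treatment; only the by-period summaries use that assignment.

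**Conclusion.** The point holds for the computed change and the shift, and no further. On scheduled samples with SAP 6.7 applied literally, subjects dosed in two or three periods contribute 0 pairs for each of the 3 hormones, against up to 24 that the collected samples could supply. The upper figure assumes that all 24 planned subjects give both samples; dropout lowers it, and the protocol itself allows for only 20 evaluable subjects out of 24.

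This is a stated rule that fails for three analytes, not merely an unspecified detail, so it is worth correcting. It is minor. It does not mean that hormone safety goes unreviewed, and it has no bearing on the primary or secondary PK analyses.

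**What to change.** - **SAP 6.7:** add that, for parameters scheduled only at Visits 1 and 5 (TSH, free T3, free T4), baseline is the last value before the first dose of trial medication.
- **SAP 6.1 and 7.8.2:** add, as an exception to analysis by treatment period, that the screening-to-end-of-trial change and reference-range shift for these parameters are shown once over all treated subjects, not under the Period 3 treatment. Define an overall column for this laboratory table, because the existing Total on-trt column in SAP 6.1 is defined for AE tables only.

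The cost is a few sentences in the SAP and one small table definition. No extra sample, visit or protocol change is needed.

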7. PLANNED ANALYSIS

The format of the listings and tables will follow the BI guideline "Reporting of clinical trials and project summaries" ([5](#)).

The individual values of all subjects will be listed. Listings will be sorted by treatment sequence, subject number and visit (if visit is applicable in the respective listing). AE listings will be sorted by assigned treatment (see [Section 7.8.1](#) below for details). The listings will be contained in Appendix 16.2 (SDL) of the CTR.

The following standard descriptive statistical parameters will be displayed in summary tables of continuous variables:

N	number of non-missing observations
Mean	arithmetic mean
SD	standard deviation
Min	minimum
Median	median
Max	maximum

For plasma concentrations as well as for all PK parameters the following descriptive statistics will additionally be calculated:

CV	arithmetic coefficient of variation
gMean	geometric mean
gCV	geometric coefficient of variation

For PK parameters the following descriptive statistics will additionally be calculated:

P10	10 th percentile
Q1	1 st quartile
Q3	3 rd quartile
P90	90 th percentile

The data format for descriptive statistics of plasma concentrations will be identical with the data format of the respective concentrations. The descriptive statistics of PK parameters will be calculated using the individual values with the number of decimal places as provided by the evaluation program. Then the individual values as well as the descriptive statistics will be reported with three significant digits in the CTR.

Tabulations of frequencies for categorical data will include all possible categories and will display the number of observations in a category as well as the percentage (%) relative to the respective treatment group. Percentages will be rounded to one decimal place. The category missing will be displayed if and only if there actually are missing values. Percentages will be based on all subjects in the respective subject set whether they have non-missing values or not.

7.1 DEMOGRAPHIC AND OTHER BASELINE CHARACTERISTICS

Only descriptive statistics are planned for this section of the CTR.

7.2 CONCOMITANT DISEASES AND MEDICATION

Concomitant diseases will be coded according to the most recent version of MedDRA. Concomitant medication will be coded according to the most recent version of the World Health Organisation – Drug Dictionary. Concomitant non-drug therapies will be coded according to the most recent version of MedDRA.

Only descriptive statistics are planned for this section of the CTR.

7.3 TREATMENT COMPLIANCE

Treatment compliance will not be analyzed as a specific endpoint. Any deviations from complete intake will be addressed in the Report Planning Meeting (cf. [Section 6.2](#)) and described in the CTR.

7.4 PRIMARY ENDPOINTS

7.4.1 Primary analysis of the primary endpoints

Primary analysis of the primary endpoints will be performed as defined in Sections 7.3.1 of the CTP.

The statistical model for the primary analysis defined in the CTP is an analysis of variance (ANOVA) model on the logarithmic scale including "treatment", "period" and "sequence" as fixed effects and "subjects within sequences" as random effect. Relative bioavailability of the study treatments will be estimated by the ratios of the geometric means

- C/A, i.e. TF2 fas/ TF1 fed
- E/A, i.e. TF2 fas/ TF1 fed, i.e.
- B/C, i.e. TF2 fed/ TF2 fas
- D/E, i.e. TF2 fed/ TF2 fas

of the primary endpoints.

Exclusion of PK parameters

The ADS ADPP contains column variables APEXC and APEXCO indicating inclusion/exclusion (APEXC) of a PK parameter and an analysis flag comment (APEXCO). All analyses based on the PKS are based on PK parameter values which are not flagged for exclusion, i.e. with APEXC equal to "Included".

Exclusion of plasma concentrations

The ADS ADPC (PK concentrations per time-point or per time-interval) contains column variables ACEXC or ACEXCO indicating inclusion/exclusion (ACEXC) of a concentration

and an analysis flag comment (ACEXCO). Exclusion of a concentration depends on the analysis flag comment ACEXCO. For example, if ACEXCO is set to "ALL CALC", the value will be excluded for all types of analyses based on concentrations. If ACEXCO is set to "DESC STATS" the value will be excluded from descriptive evaluations per planned time point/time interval. If ACEXCO contains the addition "TIME VIOLATION" or "TIME DEVIATION", the value can be used for further analyses based on actual times. If ACEXCO is set to "HALF LIFE", the value will be excluded from half-life calculation only; the value is included for all other analyses. Excluded concentration itself will be listed in the CTR associated with an appropriate flag.

Further details are given in "Noncompartmental Pharmacokinetic / Pharmacodynamic Analyses of Clinical Studies" (4) and "Description of Analytical Transfer Files and PK/PD Data Files" (6).

7.4.2 Sensitivity analysis, subgroup analysis, exploratory analysis of the primary endpoints

The same statistical model as used for the primary analysis (Sections 7.3.1 of the CTP) will be repeated for the primary endpoints but with all sources of variation ("sequence", "subjects within sequences", "period", "treatment") considered as fixed effects.

Primary PK endpoints will be assessed descriptively. The analysis of standard PK parameters is performed according to BI standards (4).

7.5 SECONDARY ENDPOINTS

7.5.1 Key secondary endpoints

This section is not applicable as no key secondary endpoint has been specified in the protocol.

7.5.2 Secondary endpoints

The secondary endpoints will be statistically analysed in the same way as for the primary endpoints. The endpoints will also be assessed descriptively. The analysis of standard PK parameters is performed according to BI standards (4).

See [Section 7.4](#) of this TSAP for details regarding exclusion of PK parameters and plasma concentrations.

7.7 EXTENT OF EXPOSURE

Descriptive statistics are planned for this section of the report, by treatment and overall.

7.8 SAFETY ANALYSIS

All safety analyses will be performed on the TS.

7.8.1 Adverse Events

AEs will be coded with the most recent version of MedDRA.

The analyses of AEs will be descriptive in nature. All analyses of AEs will be based on the number of subjects with AEs and not on the number of AEs.

For analysis, multiple AE occurrence data on the eCRF will be collapsed into one event provided that all of the following applies:

- All AE attributes are identical (lower level term, intensity, action taken, therapy required, seriousness, reason for seriousness, relationship, outcome, AESI)
- The occurrences were time-overlapping or time-adjacent (time-adjacency of two occurrences is given if the second occurrence started at most 1 hour after the first occurrence ended)

For further details on summarization of AE data, please refer to "Analysis and Presentation of Adverse Event Data from Clinical Trials" (7) and "Handling of missing and incomplete AE dates" (3).

The analysis of AEs will be based on the concept of treatment emergent AEs. That means that all AEs will be assigned to screening or on-treatment phases as defined in [Section 6.1](#). AEs will be analysed based on actual treatments, as defined in [Table 6.1: 2](#).

An overall summary of AEs will be presented. This overall summary will comprise summary statistics for the class of other significant AEs according to ICH E3 (8) and for the class of AESIs.

CTP: *The following are considered as AESIs:*

- *Hepatic injury*
A hepatic injury is defined by the following alterations of hepatic laboratory parameters:
 - *An elevation of AST (aspartate transaminase) and/or ALT (alanine transaminase) ≥3-fold ULN combined with an elevation of total bilirubin ≥2-fold ULN measured in the same blood sample, or*
 - *Aminotransferase (ALT, and/or AST) elevations ≥10 fold ULN*

The investigator had to classify on the eCRF whether an observed AE was an AESI or not.

According to ICH E3 (8) AEs classified as "other significant" need to be reported and will include those non-serious and non-significant AEs

- (i) which are marked haematological or other lab abnormalities, or
- (ii) which were reported with "action taken = discontinuation" or "action taken = reduced", or
- (iii) which lead to significant concomitant therapy as identified by the Clinical Monitor/Investigator at a Medical Quality Review Meeting.

The frequency of subjects with AEs will be summarised by treatment, primary SOC and preferred term. AEs which were considered by the investigator to be drug related will be summarised separately. Separate tables will also be provided for subjects with SAEs, subjects with AESIs and subjects with other significant AEs (according to ICH E3 (8)). The frequency of subjects with AEs and the frequency of subjects with AEs considered by the investigator to be drug related will also be summarised by maximum intensity, primary SOC and preferred term.

The SOCs and preferred terms within SOCs will be sorted by descending frequency over all treatment groups.

For disclosure of AE data on ClinicalTrials.gov, the frequency of subjects with non-serious AEs occurring with an incidence of greater than 5 % (in preferred terms) will be summarised by treatment, primary SOC and preferred term. The frequency of subjects with SAEs will also be summarised.

For disclosure of AE data in the EudraCT register, the frequency of AEs, the frequency of non-serious AEs with an incidence of greater than 5 % (in preferred terms) and the frequency of SAEs will be summarized.

For support of lay summaries, the frequency of subjects with drug-related SAEs will be summarized by treatment, primary SOC and preferred term.

If the subject reports headaches during the treatment period further information about the duration of headache, location, characteristics, and signs and symptoms were recorded. The information will be summarized with descriptive statistics.

